As a part of our original Patient-Centered Outcomes Research Institute (PCORI) proposal, we planned to educate nurses to address the observed deficiencies and misconceptions and improve their ability to communicate effectively with patients. Historically, nurse education has been done via a linear, PowerPoint-based platform with voice-over but with no interactive component (Static). A newer platform for nurse education became available for use and includes scenario-based teaching, ongoing assessment, and immediate remediation. Most importantly, it is a highly interactive product (Dynamic).

Study Objectives and Hypotheses

The Objective of this study is to improve knowledge about the benefits and importance of VTE prophylaxis and harms associated with VTE with the goal of decreasing non-administration of prescribed VTE prophylaxis.

- Primary Hypothesis: Nurse participants who receive either of these interventions will improve administration of prescribed VTE prophylaxis evidenced by a decrease in frequency of non-administered doses of VTE prophylaxis, compared with their frequency at baseline.
- Secondary Hypothesis: Nurse participants who receive the Dynamic education format will have a larger decrease in frequency of missed doses of VTE prophylaxis compared with those who participate in the Static education format.

2. Study Design

A. Study Design

- a. Cluster randomized trial

B. Study setting: Johns Hopkins Hospital, Baltimore MD

C. Eligibility Criteria

- a. All nurses permanently assigned to one of the 21 included study floors

D. Interventions

- a. Education A: An interactive dynamic learner-centric scenario-based education module with ongoing assessment, and immediate remediation (Dynamic).
- b. Education B: A linear static PowerPoint-based platform with voice-over but with no interactive component (Static).

Participants will be assigned one of two education modules based on their permanent floor assignment. The same education type will be assigned to all nurses on a single floor to mitigate issues related to contamination if nurses discuss the education with their colleagues.

E. Enrollment

- a. Nurses will be identified using our centralized education directory that associates nurses with their designated departments and hospital floors. All nurses permanently assigned to one of the 21 included study floors will be included in this study. Nurses who are not permanently associated with one of the 21 hospital floors (e.g. traveling nurse, float nurse) will be excluded from this study.

F. Randomization

- a. Nurses will be identified using our centralized education directory that associates nurses with their designated departments and hospital floors. Nurses will be cluster randomized by floor to receive one of two education modules about VTE prevention. Because of known differences between medical and surgical floors in VTE prophylaxis administration practice and culture, floors were stratified by department (i.e. medicine and surgery) for randomization. Within strata, we will use a coin toss to randomize floors into study arms.

G. Duration of Study

- a. Nurses will be given three months to complete the assigned education module. Data will be collected for one full year to include medication administration practice at baseline, during the education trial, and after the education trial.

H. Outcomes

- a. Primary Outcome measure: Proportion of non-administered doses of pharmacological VTE prophylaxis (dose level)
- b. Secondary Outcome Measures:
 - i. Nurse-reported relevance of and satisfaction with the education modules
 - ii. Proportion of doses documented as missed due to patient refusal (dose level)
 - iii. Proportion of patients with any VTE (patient level)
 1. VTE are defined by AHRQ PSI-12 diagnosis codes
 - iv. Proportion of patients with Deep Vein Thrombosis (DVT) (patient level)
 - v. Proportion of patients with Pulmonary Embolism (PE) (patient level)

Patient demographic data will be extracted from the Johns Hopkins Hospital administrative database. Pharmacologic VTE prophylaxis medication administration data will be extracted directly from electronic medication administration record in our computerized provider order entry system. Immediately following completion of the assigned education module, nurses will be asked to complete a voluntary 5-question survey to assess the relevance of and satisfaction with the education module.

3. Analytic methods

A. Baseline Characteristics

- a. Comparison of both arms to ensure similarity at baseline
- b. Descriptive analysis of baseline characteristics i.e. simple counts and proportions by trial arm

B. Multi-level mixed effects linear regression

Due to the complexity of the multilevel structure of the data (i.e. multiple doses per patient across various hospitalizations, nurses and floors), multiple imputation¹⁹ will be used to reduce the levels of hierarchical structure to the floor level and nurse level by randomly selecting one dosage per patient. By reiterating the procedure 1000 times, we will estimate the odds ratios (ORs) and 95% confidence intervals conditional on the floor and nurse.

- a. Primary analyses: Intent-to-Treat
- b. Secondary analyses
 - i. Per protocol: Nurses who complete the education where the date of completion serves as an individual inflection point for pre-post education
 - ii. Nurse-reported relevance of and satisfaction with the education modules will be analyzed using a two-sided Chi-squared test

References

1. US Department of Health and Human Services. The Surgeon General's Call to Action to Prevent Deep Vein Thrombosis and Pulmonary Embolism. <http://www.ncbi.nlm.nih.gov/books/NBK44178/>. Accessed April 5, 2014.

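### The primary hypothesis is a before-after comparison that randomisation does not protect, and no calendar-time term is named, so a background change could bias it in either direction

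*Combined protocol and SAP*

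**What the plan says.** - **Primary hypothesis** (Study Objectives and Hypotheses): nurses given either module are expected to do better, "evidenced by a decrease in frequency of non-administered doses of VTE prophylaxis, compared with their frequency at baseline". The comparator is the nurses' own earlier practice.
- **Secondary hypothesis** (same section): nurses given the Dynamic format "will have a larger decrease in frequency of missed doses of VTE prophylaxis compared with those who participate in the Static education format".
- **Randomisation** (section 2.F): "Nurses will be cluster randomized by floor to receive one of two education modules about VTE prevention". Section 2.D lists two modules, both active.
- **Timing** (section 2.G): three months are allowed to complete the module. "Data will be collected for one full year to include medication administration practice at baseline, during the education trial, and after the education trial". The lengths of the baseline and post-education periods are not given.
- **Analysis** (section 3.B): a multilevel mixed model with repeated random selection of one dose per patient, from which "we will estimate the odds ratios (ORs) and 95% confidence intervals conditional on the floor and nurse". No month, season or trend term is named. The primary analysis is labelled intent-to-treat.
- **Per-protocol analysis** (section 3.B.b.i): "Nurses who complete the education where the date of completion serves as an individual inflection point for pre-post education". This is a pre/post switch at each nurse's own date, in completers only.

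**The concern.** Every floor moves from no module to some module within one three-month window at one hospital. Anything else that changed missed doses across the hospital over that year is mixed with the education effect. Conditioning on floor and nurse removes stable differences between them, not a change over time that they share. The intent-to-treat label does not help, because education versus baseline has no randomised comparison to preserve.

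The bias can go either way. A favourable background change could be credited to education, so that the primary hypothesis is declared supported with no effect. An adverse one could hide a real benefit. The per-protocol analysis, if run without a time term, shares the bias and would not show which had happened. Because the study is described as a cluster randomised trial, readers may take the primary result for randomised evidence.

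**Working it through.** The plan gives no sample size, power, alpha or baseline rate, so there is no figure of its own to reproduce. From the documents: 12 months of data, a three-month completion window, 21 floors. Rates, dose volumes, design effect, trend, completion rate and baseline length below are all assumptions.

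**1. Trend absorbed by a pre-post split.** Assume even dose volume and a linear trend, with the split at month *d*.
- Window counted as post: midpoints *d*/2 and (*d*+12)/2. The gap is 6 months for any *d*, and 6/12 = 50% of the annual trend.
- Window dropped: post runs from *d*+3 to 12, with midpoint (*d*+15)/2. The gap is 7.5 months for any *d*, and 7.5/12 = 62.5%.

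**2. What cancels.** On the log-odds scale the change in each arm is its education effect plus the shared drift *b*. Dynamic minus Static is (e_D + b) − (e_S + b) = e_D − e_S, so *b* drops out. In the pre-post contrast it stays: pre-post OR = true OR × drift OR. With a true OR of 0.85:
- drift 0.9 gives 0.85 × 0.9 = 0.765 (exaggerated);
- drift 1.1 gives 0.935 (diluted);
- drift 1/0.85 = 1.18 gives 1.00 (hidden).

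**3. Chance of a significant fall.** z = (p0 − p1)/√(p0q0/N + p1q1/N), divided by √(design effect); P = 1 − Φ(1.96 − z); N doses in each period. Example: 12% to 11%, N = 15,000, design effect 4 gives z = 2.715/2 = 1.36 and P = 27.3%.

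| Net change between period means | Design effect | N = 5,000 | 15,000 | 40,000 |
|---|---|---|---|---|
| 12% to 11% | 4 | 12.0% | 27.3% | 60.1% |
| 12% to 11% | 1 | 35% | 77% | 99% |
| 12% to 11.5% | 4 | 6% | 10% | 19% |
| 12% to 11.5% | 1 | 12% | 27% | 59% |
| 12% to 10% | 4 | 35.9% | 79.1% | 99.5% |

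With no education effect, the first four rows are false positives from drift alone. In the other direction, a true fall from 12% to 10% offset by a one-point background rise leaves a net 12% to 11%. Detection then drops from the last row to the first. By step 1, a one-point gap between period means needs a linear trend of about two points a year; a one-point annual trend corresponds to the half-point rows.

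**4. Floor-level simulation.** Assumptions: 21 floors split 11/10, baseline 12%, 1,500 doses per floor per period, between-floor SD 0.4 and floor-by-period SD 0.1 on the log-odds scale, paired two-sided 5% test, 400 runs. With no education effect, the pre-post test rejects in 5% of runs without drift, in 85% at drift OR 0.9, and in 76% (in the harmful direction) at drift OR 1.1. The Dynamic-versus-Static difference in change rejects in about 3% to 6% at every drift tried from 0.8 to 1.2.

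**5. Completion-date analyses.** Linear approximation, nurse fixed effects, daily exposure, completion uniform over the three months, baseline of 3 to 6 months. Completers only with no time term absorbs 0.500 of the annual trend. All nurses with calendar-month effects absorbs 0.015, 0.010, 0.0075 and 0.006 at 100%, 90%, 80% and 70% completion.

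**The case against.** **The reading.** Either intervention could mean each arm against its own baseline, and section 3.B defines no pooled OR, alpha or decision rule. That is fair, but an arm-by-arm change from baseline carries the same shared drift.

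**The silence on time.** Section 3.B lists no fixed effects at all, not even arm or period, so a missing time term may be general brevity. This stands as a limit: the bias is conditional on no such term being used.

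**The plan is open about its comparator.** It never says that randomisation supports the baseline comparison, and the randomised contrast is already a separate hypothesis. True, and for that reason the first part of the fix is wording only.

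**The illustration is loosely anchored.** This stands. Nothing in the documents fixes the rate, volume, trend or clustering. The formula treats the periods as independent samples, although the same floors appear in both. At 31,500 doses per period and drift OR 0.9 it gives about 56%, against 85% in the paired simulation. Splitting the same total doses 1:3 instead of equally turns 12%, 27% and 60% into 10%, 21% and 48%. The percentages show what is possible, not what is expected.

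**The added models do not settle attribution.** Also true. A linear term cannot remove season or a step change, and the completion-date model has its own biases. They are worth adding as support, with those limits stated.

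**Conclusion.** The concern holds. The primary contrast is before-after, randomisation does not protect it, no calendar-time term is named, and the bias has no fixed direction. The firmest figure is that the contrast absorbs half of any linear annual trend (62.5% with the window dropped); it needs only the stated durations, linearity and even dose volume. How often this would change the conclusion depends on assumed inputs. This is a risk of bias, not demonstrated bias, because the documents do not show whether any background change occurred. The Dynamic-versus-Static contrast is unaffected by a change common to both arms. The plan should be changed on this point, although the order of the hypotheses can stay.

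**What to change.** 1. **Label the result.** State that the pre-post result is a non-randomised before-after association and that only the arm-by-period Dynamic-versus-Static contrast is a randomised comparison. Report a significant pooled OR as a change from baseline, and do not attribute it to education on that result alone.
2. **Add a supportive completion-date model** beside the per-protocol analysis, not in its place: all nurses, a time-varying education indicator (0 before completion, and throughout for non-completers) and calendar-month fixed effects. State its assumptions: completers and non-completers share a time trend, and the effect is constant after completion. State also that completion timing is self-selected. Section 2.D assigns modules by floor "to mitigate issues related to contamination if nurses discuss the education with their colleagues"; within a floor, the same discussion could reach nurses who have not yet completed.
3. **Add a trend-adjusted pre-post OR as a sensitivity analysis**, with the three-month window counted as post and with it dropped. Say that a linear term cannot remove season or a step change.

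**Cost.** SAP wording and two models. No new data are needed, since completion dates are already used. The SE figures below come from linear approximations that ignore the one-dose-per-patient resampling and any floor-by-time correlation.

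- *Model 2, precision:* SE about 1.5 to 2.0 times that of the completers-only analysis without a time term at 70% to 90% completion, and up to 2.5 times at 100%.
- *Model 2, bias:* if completers and non-completers differ in trend, it absorbs about 21%, 30% and 36% of the annual difference at 90%, 80% and 70% completion. If each nurse's effect takes a month to build, it estimates 69% to 83% of the full effect at 90% to 70% completion, and about 55% at 100%; completers only without a time term would recover 88% to 93%. If 25% or 50% of the effect reaches colleagues not yet educated, it recovers about 85% or 70%.
- *Model 3, window as post:* SE 1.5 times (3-month baseline) to 2.0 times (6-month baseline) the unadjusted contrast. If uptake builds linearly over the window, it recovers only 21% to 33% of the effect.
- *Model 3, window dropped:* SE 2.6 to 3.1 times the unadjusted contrast on the same data, or 2.7 to 3.4 times the full-year contrast. It recovers the full effect under that build-up.
- *Arm-by-period contrast:* with equal arms its variance is σ²/(n/2) + σ²/(n/2) = 4σ²/n against σ²/n for the pooled change, so about twice the SE. It also answers a different question.

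### The only randomised comparison (Dynamic versus Static) is framed as a difference in decreases from baseline, with no baseline adjustment named; with 21 floors, adjust the after-period contrast for each floor's baseline

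*Combined protocol and SAP*

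**What the plan says.** The Study Objectives and Hypotheses section states two hypotheses. The primary one is before-after: nurses given either module are "compared with their frequency at baseline", and the arms are not compared. The secondary one compares the arms, and says that the Dynamic group "will have a larger decrease in frequency of missed doses of VTE prophylaxis compared with those who participate in the Static education format".

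The units are the floors. Eligibility covers "All nurses permanently assigned to one of the 21 included study floors". Under 2.F, "floors were stratified by department (i.e. medicine and surgery) for randomization", and then: "Within strata, we will use a coin toss to randomize floors into study arms". Arm sizes are not given.

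Baseline data will exist for every floor, because 2.G plans a year of data covering "medication administration practice at baseline, during the education trial, and after the education trial". In the analytic methods, baseline appears only in 3.A, whose first item is "Comparison of both arms to ensure similarity at baseline" and whose second is a set of descriptive counts by arm. Section 3.B names a multilevel mixed-effects model, refitted 1000 times on one sampled dose per patient, giving odds ratios conditional on floor and nurse. It lists no fixed effects: no arm, period, arm-by-period, baseline or department term.

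**The concern.** The hypothesis wording is the only text that defines the randomised contrast, and it describes a difference between two decreases. A contrast of that kind gives baseline a fixed weight of 1. If a floor's level does not carry over fully from one period to the next, floors that start high tend to come down and floors that start low tend to come up, whatever the module. The arm that happens to start higher is then expected to show the larger decrease even if the modules are equally good.

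Because floors are randomised, any baseline difference between arms is chance. With 21 floors it can still be sizeable, and comparing the arms at baseline does not remove it from the estimate. Two things are at stake: a conditional error in favour of whichever arm started worse, and a wider interval than necessary on the one comparison that randomisation protects.

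**Working it through.** **Inputs.** From the plan: 21 floors, randomised by floor, results as odds ratios. There is no power calculation, rate, SD or correlation, so there is no figure to reproduce. Assumed: 10 and 11 floors per arm; 12% missed at baseline; OR 0.8 in both arms (9.84% after); n = 300 or 1000 patients per floor per period, one dose each; SD τ of true floor levels 0.30 or 0.45 on the logit scale; correlation ρ of a floor's true level between periods 0.5 to 0.9. Department strata are left out of the calculation.

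**Formulas (log-odds, floor level).**
- Baseline variance: Vb = τ² + 1/(n × 0.12 × 0.88)
- After-period variance: Va = τ² + 1/(n × 0.0984 × 0.9016)
- Covariance: C = ρτ²; slope of after on before: b = C/Vb
- Change contrast: variance proportional to Vb + Va − 2C
- Baseline-adjusted contrast: variance proportional to (Va − C²/Vb) × 18/17, where 18/17 = 1 + 1/17 is the cost of estimating the slope from 21 floors
- SD of the chance baseline difference: √[Vb(1/10 + 1/11)] = 0.437√Vb
- Shift of the change contrast per 1-SD imbalance: (1 − b) × 0.437√Vb

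**One cell in full** (n = 300, τ = 0.45, ρ = 0.5). Vb = 0.2025 + 0.0316 = 0.2341; Va = 0.2025 + 0.0376 = 0.2401; C = 0.1013; b = 0.433. Change variance is 0.2341 + 0.2401 − 0.2025 = 0.2717. Adjusted variance is (0.2401 − 0.0438) × 18/17 = 0.2078. The ratio is 0.2078/0.2717 = 0.76. The chance imbalance has SD 0.437 × 0.484 = 0.211, and the shift is 0.567 × 0.211 = 0.120.

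**All cells.**

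| n | τ | ρ | Variance ratio, adjusted/change | Shift per 1-SD imbalance (log-odds) |
|---|---|---|---|---|
| 300 | 0.30 | 0.5 / 0.7 / 0.9 | 0.74 / 0.82 / 0.89 | 0.096 / 0.073 / 0.051 |
| 300 | 0.45 | 0.5 / 0.7 / 0.9 | 0.76 / 0.86 / 0.95 | 0.120 / 0.083 / 0.047 |
| 1000 | 0.30 | 0.5 / 0.7 / 0.9 | 0.77 / 0.87 / 0.97 | 0.075 / 0.051 / 0.026 |
| 1000 | 0.45 | 0.5 / 0.7 / 0.9 | 0.78 / 0.89 / 0.99 | 0.105 / 0.067 / 0.028 |

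Simulation of the same set-up with binomial counts gives ratios of 0.72 to 1.00. The expected shift of the adjusted contrast is about zero. Against |ln 0.8| = 0.223, a shift of 0.026 to 0.120 is 11% to 54%, or a factor of 1.03 to 1.13 on the ratio of odds ratios.

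**Type I error and power.** A simpler simulation used normal floor means, 10 v 11 floors, two-sided 0.05 and 20,000 trials per setting. Here r is the correlation of *observed* floor means, which is lower than ρ because of sampling noise.

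| r | Type I error when imbalance exceeds 1 SD: change | same: adjusted | Power for 0.8 floor SD: change | same: adjusted |
|---|---|---|---|---|
| 0.3 | 11.1% | 5.2% | 32% | 43% |
| 0.5 | 8.4% | 4.8% | 41% | 50% |
| 0.7 | 7.5% | 4.8% | 61% | 65% |
| 0.9 | 5.6% | 5.3% | 97% | 97% |

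Over all randomisations, the change contrast's type I error is 4.8% to 5.2%.

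**Where the gain stops.** With equal variances, the ratio change/adjusted is 2(1 − r)/[(1 − r²) × 18/17]. That is 1.26 at r = 0.5, 0.99 at r = 0.9 and 0.97 at r = 0.95. For very stable floors, adjustment costs about 3% in variance.

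**The case against.** The strongest objection is that a hypothesis is not an estimator. Section 3.B lists no model terms, and nowhere does the plan say that a change score or an arm-by-period term is the test. In a linear model with baseline as covariate, the arm coefficient is the same whether the outcome is the after value or the change, so the hypothesis wording is compatible with an adjusted analysis. This stands. A reader might infer that the plan commits itself to testing change scores, and the documents do not support that. They do frame the contrast as a difference in decreases, name no adjustment, and leave the analyst free to fit the model that matches the wording.

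A reader might also infer that the module comparison is biased or its error rate inflated overall. It is not. The change contrast is unbiased over randomisation, and the error arises only given an imbalance.

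Nor is the precision loss automatic. It vanishes for large, stable floors. An observed correlation of 0.9 does, however, need nearly perfect stability of true levels: under the inputs above, ρ = 0.9 gives observed correlations of only about 0.65 to 0.86.

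Figures in percentage points would overstate the effect, because at a common odds ratio a floor that starts higher falls by more points without any regression to the mean. The plan reports odds ratios, so only log-odds figures are used here.

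Finally, the calculation uses floor summaries and omits department, while the plan fits sampled doses with floor and nurse effects. The sizes are therefore indicative. Stratification removes some imbalance between medicine and surgery, but not differences between floors within a department, and a coin toss need not balance the arms.

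**Conclusion.** The point holds as a method choice that should be changed, not as an error that invalidates the trial. The randomised comparison is worded as a difference in decreases, the baseline of every floor is collected, and nothing in the analysis section uses it to adjust the comparison.

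Under the assumed inputs, adjustment brings the variance to about 0.72 to 1.00 of that of the change contrast. It also removes a shift of about 0.03 to 0.12 log-odds per 1-SD chance imbalance. That is material when the comparison is between two active modules, whose difference may be smaller than the 0.22 used as yardstick. All the sizes depend on floor variation, floor volume and stability between periods, none of which the plan states.

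**What to change.** Keep the secondary hypothesis and state its test in 3.B: the Dynamic-versus-Static odds ratio for non-administration in the after-education period. Each floor's baseline-period log-odds of non-administration and department (the randomisation stratum) enter as fixed covariates in each of the 1000 fits.

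An approximately equivalent alternative is to model all periods with the arms constrained equal at baseline and a floor-by-period random effect. Without that effect, a floor random intercept alone assumes that floor levels carry over perfectly.

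Treat the baseline comparison in 3.A.a as descriptive; it cannot ensure similarity.

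The cost is SAP wording and two model terms, using about two of the 21 − 2 = 19 floor-level degrees of freedom. No new data are needed. At worst, variance rises by a few percent if floor levels are almost perfectly stable.

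### Floors are stratified by department but allocated by an unrestricted coin toss, and no department term is planned, so the stratification need not balance the arms

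*Combined protocol and SAP*

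**What the plan says.** The combined protocol and SAP randomises whole floors (section 2.F): "Nurses will be cluster randomized by floor to receive one of two education modules about VTE prevention". There are 21 of them; the number in each department is not given.

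Section 2.F gives the reason for stratifying, "Because of known differences between medical and surgical floors in VTE prophylaxis administration practice and culture", and states that "floors were stratified by department (i.e. medicine and surgery) for randomization". The allocation step is one sentence: "Within strata, we will use a coin toss to randomize floors into study arms". It mentions no block, pairing, allocation ratio or number of floors per arm.

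Section 3.B names a multilevel mixed model giving odds ratios and "confidence intervals conditional on the floor and nurse". It mentions no department term. Section 3.A plans a "Comparison of both arms to ensure similarity at baseline", with no rule for what follows if the arms differ.

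The hypothesis that compares the arms is the secondary one: nurses given the Dynamic format "will have a larger decrease in frequency of missed doses of VTE prophylaxis compared with those who participate in the Static education format".

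**The concern.** Stratification can protect a comparison in two ways. It can force balance, through a restriction on the allocation within each stratum, or it can enter the analysis as a model term. The plan commits to neither, although it states that department is related to the outcome.

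The primary hypothesis compares nurses with their own baseline and is little affected. The stake is the Dynamic versus Static contrast, the only hypothesis that the randomisation serves. A constant difference between medicine and surgery mostly cancels there, because the contrast compares changes within floors. Two things do not cancel:

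- the precision lost when the arms are unequal in size;
- a difference between departments in time trend, or in response to education, which a chance department imbalance carries into the arm contrast.

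Conditioning on floor does not remove the second, because it removes level differences and not differences in change.

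**Working it through.** The documents give no sample size calculation or balance target, so there is no stated figure to reproduce. The check is an exact enumeration of all allocations.

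**Inputs.** From section 2.F and the enrolment section: 21 floors, two departments, coin toss. Assumed: one independent fair toss per floor; department sizes from 5/16 to 10/11, either way round; SD of the floor-level change of 0.2 to 0.3 logit; a difference in trend between departments of 0, 0.1 or 0.2 logit; floors weighted equally.

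**Step 1: what the strata do.** With m floors in one department and 21 − m in the other, any given allocation has probability (1/2)^m × (1/2)^(21−m) = (1/2)^21. This does not depend on m, so tossing within departments is the same as tossing without them.

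**Step 2: arm sizes.**
- P(10:11) = 2 × C(21,10)/2^21 = 705,432/2,097,152 = 0.336.
- P(7:14 or worse) = 2 × P(X ≤ 7; 21, 0.5) = 0.189.
- The mean of 1/n1 + 1/n0 over non-empty splits is 0.2012, against 1/10 + 1/11 = 0.1909 for a 10:11 split. The ratio is 1.054, about 5% more variance, or √1.054 = 1.027 on the standard error.

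**Step 3: department balance.** With a of the m floors of one department in an arm of size n1, the difference in department share is |a/n1 − (m − a)/n0|.

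| Department sizes | Mean difference (points) | P(20+ points) | P(30+ points) | Maximum under even split (points) |
|---|---|---|---|---|
| 5/16 | 15.8 | 0.32 | 0.14 | 7.3 |
| 6/15 | 16.7 | 0.37 | 0.16 | 2.7 |
| 7/14 | 17.3 | 0.31 | 0.17 | 6.4 |
| 8/13 | 17.9 | 0.38 | 0.19 | 3.6 |
| 9/12 | 18.2 | 0.42 | 0.20 | 5.5 |
| 10/11 | 18.5 | 0.40 | 0.19 | 4.5 |

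As an example for 10/11, suppose 7 of the 10 floors in one department and 5 of the 11 in the other fall to Dynamic. The shares are 7/12 = 58% and 3/9 = 33%, 25 points apart. An even split gives 5/10 against 5/11, 4.5 points apart. The tosses split both departments as evenly as possible with probability only 0.11-0.12.

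**Step 4: variance of the change contrast.**
- Unadjusted: SD² × (1/n1 + 1/n0) + (trend difference × share difference)².
- Adjusted for department: SD² / Σ a(m − a)/m, summed over the two departments.

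Worked case (10/11, SD 0.2, trend difference 0.2): the mean squared share difference under tosses is 0.0527, so the variance is 0.04 × 0.2012 + 0.04 × 0.0527 = 0.01016. Under the even split it is 0.04 × 0.1909 + 0.04 × 0.0455² = 0.00772. The ratio is 1.32. Over all assumed sizes and SDs:

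| Trend difference (logit) | Tosses / even split, both unadjusted | Adjusted / unadjusted, tosses | Adjusted / unadjusted, even split |
|---|---|---|---|
| 0 | 1.054 | 1.06 | 1.001-1.007 |
| 0.1 | 1.07-1.12 | 0.995-1.04 | 0.999-1.004 |
| 0.2 | 1.13-1.32 | 0.84-0.98 | 0.98-0.999 |

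**The case against.** **The sentence admits another reading.** A toss within pairs, or one toss deciding which half of a department receives which module, also fits the wording and would achieve balance. This stands as a limit: the probabilities above apply only to one toss per floor. What is certain is that no restriction is stated.

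**Section 3.B lists no fixed effects at all, not even arm or period.** True. The missing department term is therefore part of an unspecified model and not a decision to ignore the strata. Nothing in the plan commits to such a term either, so naming it contradicts nothing.

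**The consequence is small and rests on assumptions.** Largely fair. The stated reason for stratifying concerns practice and culture, not different trends. With no trend difference the loss is about 5% of variance. The 32% figure needs the corner case of SD 0.2, trend difference 0.2 and sizes 10/11; at SD 0.3 and 0.1 logit it is 7-8%. Doses and nurses per floor are not given, so equal weighting of floors is a simplification.

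**Adjustment after unrestricted tosses may not pay.** On average it costs about 6% with no trend difference, is roughly neutral at 0.1 logit and gains clearly only at 0.2. That is an argument for restricting the allocation first. It does not remove the case for an analysis that follows the randomisation strata, since the cost is bounded and adjustment guards against a badly imbalanced draw.

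**Conclusion.** The concern holds. As written, the plan gives a reason to stratify but no mechanism, in allocation or analysis, by which the stratification takes effect. The randomisation remains valid and unbiased on average; the issue is chance imbalance and precision with only 21 clusters, and it falls on the secondary hypothesis. The likely loss is modest if departments change alike over time and becomes material only if they do not, on which the documents give no figure. All sizes depend on reading the sentence as one toss per floor and on the assumed department sizes, SDs and trends. The remedy costs almost nothing before allocation, so the change is worth making.

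**What to change.** **Section 2.F.** State the number of floors in each department. Within each department, put the floors in random order and assign half to each arm, with one toss for the odd floor. Since 21 is odd, exactly one department has an odd number, so the arms are always 10:11. If the toss was meant to act on pairs or pre-set halves, say so.

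**Section 3.B.** Add department and department-by-period as fixed effects. If conditioning on floor means floor fixed effects, the department main effect is redundant because floors nest in departments, and only the department-by-period term is needed.

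**If floors are already allocated.** Report floors per arm by department and make the model change only. Its variance cost with no trend difference can then be computed from the actual counts with the step 4 formulas, without outcome data.

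**Cost.** None for the allocation if it has not yet happened: a random list replaces the tosses. The model terms are SAP wording and use one or two degrees of freedom. If departments do not drift apart, they add at most 0.7% to the variance under the even split and about 6% on average under independent tosses.
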